5.2 Timing of Analyses

Analysis of the study results will be ongoing throughout enrollment. Regular case review by the Data and Safety Monitoring Board (DSMB) and Sponsor will occur throughout enrollment.

DSMB data review will be instituted as follows:

- For the first four (4) Subjects, procedural reports will be provided to FDA and the DSMB Chairman within 5 working days of endovascular treatment and will include available procedural narratives, reports and any preliminary Adverse Events (AEs.
- Reporting Subject and device performance data to the DSMB following the endovascular treatment of every two (2) Subjects through patient 20 and every five (5) patients for patient 20-30, including the available 1 month follow-up visit data for preceding cohorts.

- Reports will include information on Subject baseline characteristics, deaths, and a summary of all serious adverse events such as paraplegia, paraparesis, stroke, and aortic rupture.
- Reports will also include observed device and/or procedure related adverse events such as deployment anomalies, branch lumen obstruction or occlusion, adverse events that result in secondary interventions for additional device implantation, and adverse events that result in conversion to open surgical repair.
- Reports provided to the DSMB will be submitted to the FDA as IDE supplements and a summary will be sent to each participating Site IRB.

The primary analysis will occur when enrollment is complete, and all available enrolled Subjects have completed the 1 month follow up assessment. A final DSMB review will be conducted when all enrolled Subjects have reached the 1 year follow-up window. Serial analyses of long-term results will occur during the follow-up period. No adjustments to the overall alpha level will be made since this is an exploratory study designed to evaluate basic feasibility.

5.3 Analyses Supporting Primary Objective(s)

Primary and secondary endpoint analyses will be summarized for main reporting efforts in order to support the study objective. Analysis populations will be as described in Section 5.1.

5.3.1 **Primary Endpoint**

5.3.2 Secondary Endpoint – Technical Success

The individual components of technical success will also be summarized similarly. In addition, whether the primary technical success was assisted primary or secondary (see Endpoint Definitions Section 2.3.3) will also be summarized. All components of the technical success assessment and whether the technical success was assisted primary or secondary are asked in the treatment CRF.

5.3.3 Secondary Endpoint - MACCE

Kaplan Meier methodology will be used to estimate the overall MACCE event rate through the following specified time intervals: 30 days, 180 days (6 months), and 365 days (12 months). A Subject experiencing a MACCE event will have their time be equal to their earliest MACCE event onset; a Subject not experiencing a MACCE event will be censored at their last reported date of contact. This analysis will be performed for each MACCE component (see Endpoint Definitions Section 2.3.3) as well. Endpoint MACCE events will be death or CEC-adjudicated adverse events meeting the endpoint definitions (assessed on the CEC CRF). All possible adverse events that could meet the endpoint definition will be sent to the CEC for adjudication.

In addition to Kaplan Meier methodology, tables will be prepared with time intervals and the incident MACCE event rate will be reported in each time interval window. Denominators for the time windows will be the number of Subjects remaining in follow-up as of the beginning of the time interval window. Time intervals for these tables will be as follows: 0 days, 1-30 days, 31-180 days, 181-365 days, 366-731, 732-1096, 1097-1461, 1462-1826.

MD133254 Statistical Analysis Plan Template

5.3.4 **Secondary Endpoint – Aorta-Related Mortality**

The aorta-related mortality endpoint (see Endpoint Definitions Section 2.3.3) will be determined by CEC adjudication using a specific question asked on the CEC CRF.

For analysis of the aorta-related mortality endpoint, Kaplan Meier methodology will be used to estimate the aorta-related mortality rate through the following specified time intervals: 30 days, 180 days (6 months), and 365 days (12 months) and annually thereafter. Subjects without an aorta-related death reported before the end of the time period of interest will be censored at the Subject's last reported contact date or the end of the time period of interest, whichever date is earlier.

5.3.5 **Secondary Endpoints – Device Migration and Endoleak**

Tables (one for device migration and one for endoleak) will be prepared with time intervals and the incident event rate will be reported in each time interval window (using either the corresponding imaging date or adverse event onset date). Denominators for the time windows will be as specified in Section 5.1. An endpoint event (endpoint failure) will be reported from a Site-reported adverse event meeting the endpoint definitions. Time intervals for these tables will be the analysis windows shown in Table 1. In addition, endoleak rates will also be reported by endoleak type.

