2.1.1 Primary Objective(s)

- To assess the feasibility of treating DeBakey Type I/II aortic dissections with the GORE® **Ascending Stent Graft**
- 2. Refine patient selection for future clinical investigations
- 3. To estimate boundary conditions in DeBakey Type I/II aortic dissection patients which can be used for subsequent device development efforts including:
 - Aortic compliance
 - Cardiac and respiratory motion

2.2 **Design Summary**

This study is a prospective, multicenter, non-randomized single-arm study to assess the feasibility of the treatment of DeBakey Type I/II aortic dissections with the GORE® Ascending Stent Graft Device.

A maximum of 9 Clinical Investigative Sites (referred to as "Sites" in the remainder of this document) in the United States will participate in this study. A total of 30 patients will be enrolled in this study.

Patients may be enrolled into the study provided all inclusion and no exclusion criteria are met as specified in Section 4 of the study Protocol.

2.3 **Study Endpoints**

2.3.1 **Primary Endpoint**

The primary endpoint is all cause mortality through 30 days post-procedure.

2.3.2 **Secondary Endpoints**

Secondary endpoints include the following:

- Successful dissection treatment (technical success), to include:
 - Successful access to the aorta (transfemoral or retroperitoneal)
 - Successful delivery of all required device components to the aorta and/or branch vessel
 - Successful deployment of all required device components in their intended location

CONFIDENTIAL INFORMATION

MD133254 Statistical Analysis Plan Template

- o Successful retrieval of device delivery system
- Exclusion of the primary entry tear of the aortic dissection based on completion angiography
- Patent Side Branch Component (if used as part of primary procedure) based on completion angiography
- Major Adverse Cardiovascular and Cerebrovascular Event (MACCE) assessed through 30 days, 6 months, and 12 months.
- Individual MACCE components through 30 days, 6 months, and 12 months.
- Aorta-related mortality
- Device migration assessed at 1 month, 6 months, and 12 months
- Endoleak assessed at 1 month, 6 months, and 12 months

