5.4 Adverse Events

Adverse events (AEs) will be summarized for main reporting efforts. Adverse events are defined as any untoward medical occurrences in a Subject whether device-related or not. All AEs will be recorded on the appropriate CRF and documented in the Subject's permanent medical record. The Investigator at each Site is ultimately responsible for reporting all AEs to the Sponsor, as well as to the IRB, as applicable.

Adverse events will be summarized by incidence (i.e. a specific AE will not be counted more than once for a Subject within each window) in each analysis time window for each Subject. The denominator for each window will be calculated as the number of enrolled Subjects remaining in follow-up as of the beginning of the analysis window (Subjects must have an initial procedure date). At a minimum, separate summaries by AE relationship and severity will be prepared.

Partial dates (month and/or day unknown) for AE onset and AE resolution dates will be allowed for analysis. Exact imputation logic will be documented in the appropriate specifications document. In general, partial dates will be imputed to be most conservative with regards to timing after initial procedure date.

Selected AEs will be reviewed by the independent CEC and adjudicated with regard to device and/or procedure relationship and severity. Specific AEs of clinical interest in this Subject population will include, but are not limited to: death-related AEs, stroke, paraplegia/paraparesis, and MACCEs. Reported AEs which potentially meet the definition of AEs of clinical interest will be referred to the CEC for review and adjudication to the study Protocol's definitions provided for these events. The adjudicated opinion of the CEC will also be used in analysis and reporting of adverse event data.

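### While a window is still open at the data cut, crude rates in the MACCE tables after day 365 and in the AE summaries run low

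*Combined protocol and SAP*

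**What the plan says.** SAP 5.3.3 gives MACCE two presentations. The first is Kaplan-Meier, overall and by component, at 30, 180 and 365 days; for it, "a Subject not experiencing a MACCE event will be censored at their last reported date of contact". The second, additional to the first, is a set of tables of incident events in eight consecutive windows. Four of these start after day 365: 366-731, 732-1096, 1097-1461 and 1462-1826. For these tables, "Denominators for the time windows will be the number of Subjects remaining in follow-up as of the beginning of the time interval window".

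SAP 5.4 summarises adverse events by window, with a denominator of "the number of enrolled Subjects remaining in follow-up as of the beginning of the analysis window". No Kaplan-Meier analysis of adverse events is stated.

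On timing, SAP 5.2 says "The primary analysis will occur when enrollment is complete, and all available enrolled Subjects have completed the 1 month follow up assessment", then "A final DSMB review will be conducted when all enrolled Subjects have reached the 1 year follow-up window", and "Serial analyses of long-term results will occur during the follow-up period". The Protocol Summary expects 2 years of accrual and follow-up to 5 years after the last enrolment.

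MACCE as an endpoint (SAP 2.3.2) is "Major Adverse Cardiovascular and Cerebrovascular Event (MACCE) assessed through 30 days, 6 months, and 12 months". Aorta-related mortality has Kaplan-Meier at the same three times and then annually (5.3.4). All-cause mortality over time also uses Kaplan-Meier (5.5.4). SAP 2.4 plans no formal tests.

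**The concern.** With staggered entry, a cut made before the last subject finishes a window catches some subjects part-way through it. The stated rule counts each of them as one full subject in the denominator, while any event they have later in the window cannot yet be in the numerator. If the timing of the cut is unrelated to risk, the crude rate is then low in expectation, which is the favourable direction.

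Two outputs have no visible censoring-adjusted companion: non-fatal MACCE after day 365, and adverse events in any window still open. A reader of a serial report could take a half-observed window for a low event rate. In a descriptive feasibility study the reported rates are the main product, and SAP 2.1.1 includes refining patient selection for later investigations among its objectives.

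**Working it through.** The plan gives no event rate or worked figure to reproduce, so this is an illustration of the rule.

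**Inputs from the documents:** 30 subjects; 2-year accrual; the SAP 5.3.3 windows; cuts when the last subject reaches 1 month and 1 year (SAP 5.2).

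**Assumptions:** uniform entry over 24 months, constant hazard within a window, no dropout, no removal for earlier events. Days 366-731 are treated as months 12-24. Full-window risk p is 5%, 10% or 20%.

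**Formula.** Let λ = -ln(1 - p), and let f be the fraction of the window observed. A subject contributes an expected 1 - exp(-λf) events. For subjects still inside the window, f is uniform on 0 to 1, so their mean contribution is m = 1 - p/λ. A completer contributes p.

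- p = 20%: λ = 0.2231, m = 1 - 0.2/0.2231 = 10.4%
- p = 10%: λ = 0.1054, m = 5.1%
- p = 5%: λ = 0.0513, m = 2.5%

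**Primary analysis (month 25), months 12-24.** Entered: 30 × 13/24 = 16.25. Completed: 30 × 1/24 = 1.25. The crude rate is (12/13)m + (1/13)p.
- p = 20%: 9.57% + 1.54% = 11.1% (ratio 0.56)
- p = 10%: 5.5% (ratio 0.55)
- p = 5%: 2.7% (ratio 0.54)

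**All subjects at 1 year (month 36), months 12-24.** Entered 30, completed 15. The crude rate is 0.5m + 0.5p.
- p = 20%: 15.2% (ratio 0.76)
- p = 10%: 7.5% (ratio 0.75)
- p = 5%: 3.8% (ratio 0.75)

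**Same cut, months 24-36.** Entered 15, completed 0. The crude rate is m, which is 10.4% when p = 20% (ratio 0.52).

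**All subjects at 2 years, months 12-24.** Everyone has completed the window, so the ratio is 1.00.

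The ratios hardly depend on p. They do depend on accrual and hazard shape, as these results for p = 20% show:

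| Accrual | Months 12-24, primary analysis | Months 12-24, all at 1 year |
|---|---|---|
| 2 years | 11.1% | 15.2% |
| 3 years | 15.4% | 16.8% |
| 4 years | 16.9% | 17.6% |

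Over 2 to 4 years of accrual, front- to back-loaded entry, and falling to rising hazard, the two cells range over 4.1-19.0% and 9.4-19.8%. The size varies widely; the direction does not.

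**Adverse events.** If the AE windows match the MACCE ones (Table 1 is not visible), the primary-analysis rates with p = 20% in each window are:
- days 31-180: (19/24)(20%) + (5/24)(10.4%) = 18.0%
- days 181-365: (13/19)(20%) + (6/19)(10.4%) = 17.0%

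**Closed window with dropout d per year.** Put μ = -ln(1 - d). The crude rate is λ/(λ+μ) × [1 - exp(-(λ+μ))]. With p = 20% this gives 19.5%, 19.0% and 18.0% for d = 5%, 10% and 20%.

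**Bias against noise.** At p = 20% the shortfall at the primary analysis is 16.25 × (20% - 11.1%), about 1.4 events. At 1 year it is 30 × (20% - 15.2%), also about 1.4. Exact 95% intervals are 1.6-38.3% for 2/16 and 5.6-34.7% for 5/30, so sampling error exceeds the bias.

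**Would Kaplan-Meier help?** In simulation at p = 20%, 2-year accrual and the 1-year cut, the within-window Kaplan-Meier estimate averages 20.0% for months 12-24, against 15.2% crude. For months 24-36, which nobody has completed, it averages 18.0% against 10.4%. An estimate at a time that no subject has reached is therefore still low.

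**The case against.** The strongest reply is that the tables already reveal most of this. The windows are contiguous, so the next window's denominator is the number who came through the previous one still in follow-up. Denominators of 30 and then 15 warn the reader. That stands in part. It requires the denominators to be printed, it does not separate subjects who have not yet reached the next window from those who died or withdrew, and it fails for the last window.

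Other points stand in full. The SAP defines a crude incidence with a disclosed denominator and never calls it a full-window risk. No text says that the primary analysis will report days 366-731, and the dates of the serial analyses are not given. Table 1 and the content of 5.5.1, 7.1-7.2 and 8.1-8.3 are not visible, so a footnote or layout that deals with open windows cannot be excluded.

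A reader might also infer three stronger things that the documents do not support:

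- **That a stated endpoint is biased.** MACCE is an endpoint only to 12 months, where Kaplan-Meier with censoring is specified. The primary endpoint, 30-day mortality, does not use this rule. Late deaths have their own Kaplan-Meier analyses.
- **That the DSMB is shown understated rates.** SAP 5.2 says "Reports will include information on Subject baseline characteristics, deaths, and a summary of all serious adverse events" and adds device- and procedure-related events. It does not mention window rates.
- **That the 5-year results stay understated.** The open-window effect ends when the window closes; only the small dropout effect remains.

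**Conclusion.** The point holds, and it is minor. In the supplementary MACCE tables after day 365 and in the AE window summaries, the stated denominator gives a crude rate below full-window risk, in expectation, at any analysis run while the window is open. Under 2-year uniform accrual, constant hazard and no dropout, days 366-731 show about 55% of the true risk at the primary analysis, if reported then, and about 75% when all subjects have reached 1 year. Those sizes rest on assumptions that the documents do not supply. The direction needs only censoring unrelated to risk, and a single observed rate from so few subjects can fall on either side.

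Confidence is medium, mainly because the AE windows and the table layouts cannot be seen.

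**What to change.** 1. In SAP 5.3.3, extend the MACCE Kaplan-Meier estimates, overall and by component, annually to 5 years, as 5.3.4 already does for aorta-related mortality. Print the number at risk, and give no estimate at a time that no subject has reached. The censoring rule in 5.3.3 already supports this.
2. In the 5.3.3 and 5.4 window tables, keep the crude incidence. Unless the layout already does so, print the number who completed each window beside the number entering it, and mark as incomplete any window still open at the cut.

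The cost is SAP wording and a little table code, with no new data. Late estimates will be slightly less favourable, and they will rest on few subjects with wide intervals.

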5.5.4 Mortality

For analysis of all-cause mortality over time (i.e. at 1-year), Kaplan Meier methodology will be used. Subjects without death reported before the end of the time period of interest will be censored at the Subject's last reported contact date or the end of the time period of interest, whichever date is earlier.

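### SAP Section 5.3.4 censors non-aortic deaths in a Kaplan-Meier estimate of aorta-related mortality, so the reported rate can overstate the share of subjects who die of aortic causes (minor, mainly at the annual time points)

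*Combined protocol and SAP*

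**What the plan says.** SAP Section 5.3.4 states that "Kaplan Meier methodology will be used to estimate the aorta-related mortality rate" at 30, 180 and "365 days (12 months) and annually thereafter". The censoring rule reads "Subjects without an aorta-related death reported before the end of the time period of interest will be censored", and the censoring date is the "last reported contact date or the end of the time period of interest, whichever date is earlier". Whether a death is aorta-related "will be determined by CEC adjudication using a specific question asked on the CEC CRF". Section 5.1 includes every enrolled subject with an attempted procedure in this analysis.

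Three other places matter:
- Section 5.5.4 handles deaths from any cause: "For analysis of all-cause mortality over time (i.e. at 1-year), Kaplan Meier methodology will be used".
- Section 2.4 plans no formal tests, only description with confidence intervals.
- Section 5.2 calls the trial an "exploratory study designed to evaluate basic feasibility".

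The visible text mentions no cumulative incidence function or other competing-risk method. Sections 2.3.3 (endpoint definitions), 5.5.1 (sensitivity analysis) and 8.1 to 8.3 (tables, listings, figures) appear in the public copy as headings only.

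**The concern.** Kaplan-Meier treats a censored subject as still able to have the event later, at the same hazard as those who remain under observation. That is reasonable for a subject who leaves follow-up alive. It is not for one who has died of something else. Each non-aortic death shrinks the risk set, so every later aortic death carries more weight than its share of the subjects treated.

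The result estimates aorta-related mortality net of other deaths, as if those deaths could not happen. A reader will more naturally take a mortality rate in 30 treated subjects as the share who died of aortic causes. Because no test is planned, the estimate and its interval are themselves the reported finding. The Protocol Summary selects subjects at high surgical risk and follows them for 5 years, so non-aortic deaths are plausible, and their effect accumulates towards the later annual estimates.

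**Working it through.** **Inputs from the documents.** N = 30 (SAP 2.2); Kaplan-Meier with the censoring rule above, at 30, 180 and 365 days and then annually (5.3.4); 5 years of follow-up (Protocol Summary). No expected aortic or non-aortic death rate is visible, so there is no planned figure to reproduce. Every rate below is an assumption.

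**Formulas.** With d aortic deaths among n at risk at each death time:
- 1-KM = 1 − ∏(1 − d/n).
- Aalen-Johansen cumulative incidence = Σ S(t−) × d/n, where S is survival from death of any cause.

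S is never larger than the aortic-only Kaplan-Meier curve, so 1-KM is never the smaller of the two. They are equal when no non-aortic death precedes an aortic one.

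**1. Constant proportion.** Let M be all-cause mortality and s the aortic share of deaths. Then the cumulative incidence is s × M and 1-KM = 1 − (1 − M)^s. For s = 0.5:

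| M | Cumulative incidence | 1-KM | Excess (points) |
|---|---|---|---|
| 10% | 5.0% | 5.1% | 0.1 |
| 20% | 10.0% | 10.6% | 0.6 |
| 30% | 15.0% | 16.3% | 1.3 |
| 40% | 20.0% | 22.5% | 2.5 |
| 60% | 30.0% | 36.8% | 6.8 |

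At M = 40%, 1 − 0.6^0.5 = 0.225. With s = 0.25 or 0.75 the excess at M = 40% is 2.0 or 1.8 points. The excess reaches one subject in 30 (3.3 points) at M of about 45% for s = 0.50, 50% for s = 0.25 and 52% for s = 0.75.

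**2. Early aortic deaths.** Keep 20% aortic and 20% other deaths by 5 years, with the other deaths evenly spread. Let a fraction f of the aortic deaths fall in the first 30 days. About 0.3% of subjects die of other causes in those 30 days (20% × 30/1826); leaving that out of the first step:

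KM at 5 years ≈ (1 − 0.2f) × [0.6 / (1 − 0.2f)]^r, with r = 0.2(1 − f) / [0.2(1 − f) + 0.2].

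- f = 0.5: 0.90 × (0.6/0.90)^(1/3) = 0.786, so 1-KM = 21.4%, excess 1.4 points.
- f = 0.8: 0.84 × (0.6/0.84)^(1/6) = 0.794, so 1-KM = 20.6%, excess 0.6 points.
- f = 0.9: 0.82 × (0.6/0.82)^(1/11) = 0.797, so 1-KM = 20.3%, excess 0.3 points.

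Including the 0.3% leaves these excesses unchanged to one decimal.

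**3. Order of deaths in 30 subjects.** Six aortic and six other deaths, complete follow-up, observed aortic share 6/30 = 20.0%:
- Other deaths last: 1-KM = 6/30 = 20.0%.
- Random order: 22.5% on average (20,000 orderings).
- Other deaths first: 6/24 = 25.0%, excess 5.0 points.

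**4. By time point.** A separate check used piecewise-constant hazards: assumed cumulative hazards of 0.05 to 0.20 per cause in the first 30 days, then 0.03 to 0.05 per year aortic and 0.05 to 0.15 per year non-aortic. The excess was 0.1 to 1.6 points at 30 days, 0.3 to 2.5 at 365 days and 2.1 to 9.0 at 5 years. The 9.0 belongs to a scenario with 74.9% all-cause mortality at 5 years.

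**Scale.** The exact (Clopper-Pearson) 95% interval for 6/30 is 7.7% to 38.6%, about 31 points wide.

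**The case against.** The strongest case on the other side is that this changes little. The endpoint is secondary, the study is exploratory, nothing is decided on the estimate, all-cause mortality is shown separately, and the direction against the cumulative incidence is to overstate aortic deaths. The excess is small beside the sampling error. All of this stands, and it is why the point is minor.

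The size also depends on timing. The 30-day primary endpoint makes early clustering of aortic deaths worth considering, and step 2 shows that such clustering shrinks the excess. This stands too: the documents fix the direction but not the size.

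It can also be argued that naming Kaplan-Meier with an explicit censoring rule already identifies the net estimator, so a label would be enough. That is partly right. But a net probability is not what most readers will take the rate to be, and the better estimate needs no new data.

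Finally, SAP 5.4 sends death-related adverse events to the Clinical Events Committee (CEC), and 5.4.4 asks for the cause of death as the reported event. Deaths by cause may therefore be recoverable from other outputs, but nothing visible promises a table of them.

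Four stronger readings are tempting and are not supported:
- That 1-KM must exceed the true share of aortic deaths. The ordering is against the Aalen-Johansen estimate on the same data. Aortic deaths missed after last contact would lower both estimates and could put 1-KM below the true share.
- That the plan contains no competing-risk output. Sections 5.5.1 and 8.1 to 8.3 cannot be read in the public copy.
- That the MACCE components are mishandled. Section 5.3.3 says "This analysis will be performed for each MACCE component", but the component list in 2.3.3 is not public, and the section does not say how a death without the component is treated.
- That the primary endpoint, overall MACCE or all-cause mortality is affected. All deaths count as events there, so no competing death arises.

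**Conclusion.** The point holds as a minor one. As written, Section 5.3.4 censors non-aortic deaths, so its estimate is at or above the cumulative incidence and exceeds it whenever an aortic death follows a non-aortic one. At an assumed 20% aortic and 20% other deaths by 5 years, the excess runs from nil (other deaths last) to 5 points (other deaths first, 30 subjects), and is about 2.5 points under constant proportion. It is small through 12 months in the scenarios examined and grows at the annual time points. Heavier competing mortality would enlarge it. The direction follows from the text and the algebra; the sizes rest entirely on assumed rates and timing. Taking the estimate as the share of treated subjects also requires that loss to follow-up be non-informative, which is a separate matter that changing the estimator does not address.

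**What to change.** In SAP Section 5.3.4, make the Aalen-Johansen cumulative incidence of aorta-related mortality, with non-aortic death as the competing event, the main estimate, and give its confidence interval. If Kaplan-Meier is also shown, label it as net of other deaths. Keep Kaplan-Meier for overall MACCE and all-cause mortality. If any MACCE component in Section 2.3.3 is non-fatal, apply the same estimator to it, with death without that event as the competing event. If Section 5.5.1 or 8.1 to 8.3 already provides a competing-risk estimate, make that the main one.

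The cost is SAP wording and minor programming. Death dates and the CEC answer on aorta-related death are already collected. The reported figure may be slightly lower than under the current text.

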2.5 Sample Size Assumptions

2.6 Sample Size Calculations

3.0 **Study Treatment Arms**

3.1 **Test Arm**

The test arm are those Subjects enrolled in this study for the treatment of DeBakey Type I/II aortic dissections (see Section 4 of the study Protocol).

3.2 **Control Arm**

There is no control arm in this study.

4.0 **Study Data Collection**

4.1 **Data Collected**

Data will be collected in Case Report Forms (CRFs) and include the following:

- Demographics
- · Eligibility (Inclusion/Exclusion) Criteria
- Medical History
- Risk Assessment
- · Subject Physical Evaluations and Vitals
- · Modified Rankin Scale Assessments
- SF-36® Questionnaire
- · Pre-Imaging Assessment
- Treatment Assessment
- Interval (Post) Imaging Assessments
- Device Accountability (Treatment and Post-Treatment)
- Planned Interventions
- · Study Completion/Discontinuation/Compliance
- Adverse Events (AEs) and Treatments (including Reinterventions)
- · Clinical Events Committee (CEC) Evaluations

[figure not shown]

CONFIDENTIAL INFORMATION

MD133254 Statistical Analysis Plan Template

Revision#: 1 Doc Type: GC Page 6 of 17

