4.6 Imaging

5.0 Statistical Analyses

5.1 Analysis Populations

All enrolled Subjects with an attempted initial procedure (have non-missing initial procedure date) will be included in analysis as follows:

- Primary Endpoint: all Subjects will be included; Subjects without known mortality status through 30-days will be considered failures for this (i.e. assumed dead for the primary endpoint analysis).
- Secondary Endpoint of technical success: all Subjects will be included; any Subject missing evaluation on this will be counted as a failure for this endpoint.
- Secondary Endpoint (MACCE, MACCE components, and aorta-related mortality): all Subjects will be included.
- Secondary Endpoints (device migration, endoleak): Subjects with known status (have had imaging done or endpoint event reported) at each follow-up window will be included; an endpoint event (endpoint failure) will be reported from a Site-reported adverse event. Subjects without imaging reported in a window but with an adverse event meeting the endpoint definition in a window will count as having an endpoint event for that window. Subjects without imaging reported in a window and with no endpoint event reported in window will not count towards the denominator for that window.

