5.5.3 Imaging Analysis

All imaging data will be Site-reported. The Sites will provide review of imaging data collected during the study at pre-treatment and follow-up.

CONFIDENTIAL INFORMATION

MD133254 Statistical Analysis Plan Template

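### Endoleak and migration events are taken from site-filed adverse events while imaging fills the denominator, so a finding recorded only on imaging would count as event-free

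*Combined protocol and SAP*

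**What the plan says.** SAP Section 2.3.2 lists device migration and endoleak as secondary endpoints at 1, 6 and 12 months. The Protocol Summary schedules a CTA of the chest at each of those times.

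- **Numerator.** Section 5.3.5: "An endpoint event (endpoint failure) will be reported from a Site-reported adverse event meeting the endpoint definitions". Section 5.1 gives the same rule: "an endpoint event (endpoint failure) will be reported from a Site-reported adverse event".
- **Denominator.** Section 5.1: "Subjects with known status (have had imaging done or endpoint event reported) at each follow-up window will be included". A subject with no imaging but a qualifying AE is added as an event. For the rest: "Subjects without imaging reported in a window and with no endpoint event reported in window will not count towards the denominator for that window".
- **Timing.** Section 5.3.5 assigns results to windows "using either the corresponding imaging date or adverse event onset date".
- **Imaging data.** Section 4.1 lists "Interval (Post) Imaging Assessments" among the case report form (CRF) data, as a separate item from adverse events. Section 5.5.3 says "All imaging data will be Site-reported" and "The Sites will provide review of imaging data collected during the study at pre-treatment and follow-up".

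Under Section 2.4 there is no formal testing; results are descriptive, with confidence intervals.

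**The concern.** The two halves of the rate come from different sources. Having a scan makes a subject's status known, but the result of the scan does not set that status; the AE form does. A site might see an endoleak or some device movement, record it on the imaging assessment, judge it benign and file no AE. The rule then scores that subject as a success.

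Other endpoints are handled differently. Technical success comes from dedicated questions on the treatment CRF, and a missing evaluation counts as failure (Sections 5.1 and 5.3.2). Unknown 30-day vital status counts as death (Section 5.1). For endoleak and migration in an imaged subject, the absence of an AE counts as event-free.

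Section 5.3.5 also promises endoleak rates by type. The AE items listed in Section 5.4.3 have no separate field for type, so an AE-based count would have to take it from the description or its coding.

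At stake are the two imaging-based device-performance endpoints of a feasibility study whose stated aims include refining patient selection and informing device development (Section 2.1.1). If sites differ in when they call an imaging finding an AE, the pooled rate partly measures that habit. The planned confidence intervals do not reflect it.

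**Working it through.** The visible documents give no endoleak or migration rate to reproduce, so the check is of the scoring rule, followed by an illustration of size.

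**Step 1: apply the rule to each case** (Sections 5.1 and 5.3.5).

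| Imaged in window | Qualifying AE filed | In denominator | Scored as event |
|---|---|---|---|
| Yes | Yes | Yes | Yes |
| No | Yes | Yes | Yes |
| No | No | No | – |
| Yes | No | Yes | No, whatever the imaging shows |

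The last row is the problem. The wording on imaging date or AE onset date does not change it: that wording says which window a result falls in, while the sentence defining an event names only the AE.

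**Step 2: direction.** Compare the rule with one that counts an event from imaging or an AE. Both rules have the same denominator, because an imaging finding requires imaging. The events differ only by findings with no AE, which the current rule drops. Relative to the either-source rule, the reported rate is therefore equal or lower, never higher.

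**Step 3: size.** Let p be the proportion of imaged subjects with a qualifying finding and s the share of those findings filed as AEs. With no AE-only events:

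expected reported rate = p × s

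Neither p nor s is in the documents. Assume 28 subjects imaged in a window, of the 30 planned, with 8 positive. Exact (Clopper-Pearson) 95% limits for x events in n are the 2.5% point of Beta(x, n − x + 1) and the 97.5% point of Beta(x + 1, n − x).

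| Share filed (assumed) | Reported | Rate | Exact 95% CI |
|---|---|---|---|
| 100% | 8/28 | 28.6% | 13.2 to 48.7 |
| 75% | 6/28 | 21.4% | 8.3 to 41.0 |
| 50% | 4/28 | 14.3% | 4.0 to 32.7 |
| 25% | 2/28 | 7.1% | 0.9 to 23.5 |

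Each unfiled finding lowers the rate by 1/28 = 3.6 percentage points.

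**Step 4: other assumed rates.** With half filed, p of 10%, 20% and 30% gives expected reported rates of 5%, 10% and 15%. With a quarter filed, they are 2.5%, 5% and 7.5%. At p = 20% with all 30 subjects imaged, the chance of reporting no event at all is (1 − 0.20)^30 = 0.001 if every finding is filed, and (1 − 0.20 × 0.25)^30 = 0.95^30 = 0.215 if a quarter are filed.

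**The case against.** The strongest reply is that the missing link may exist where it cannot be read. No text is visible under Section 2.3.3 (endpoint definitions), Section 4.6 (imaging) or Section 5.5.1 (sensitivity analysis), and the protocol body is not available. A requirement there to file an AE for every endoleak or migration seen on imaging would remove the bias. This stands. A reader might infer that the plan has no such requirement, but the documents do not support that; one can say only that the visible text contains none.

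Second, Section 5.4 defines AEs broadly and says all are to be recorded. An endoleak meeting the endpoint definition plausibly qualifies, and leaving it unfiled would then be under-reporting. This narrows the gap without closing it, because the section does not say that imaging findings are AEs.

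Third, the fields on the imaging form are not shown. That it records endoleak and migration is an inference from Sections 4.1 and 5.5.3, and the low cost of the fix depends on it.

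Three stronger readings should also be set aside:

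- *The rule can only lose events.* This is true against an either-source rule, not against the truth, since an over-called AE would add an event.
- *These events are barred from the Clinical Events Committee (CEC).* Section 5.4 leaves its list of events of clinical interest open, and the protocol's CEC section is not visible. However, Section 5.4 refers reported AEs, so it shows no route to the CEC for an unfiled finding.
- *A single site drives the pooled rate.* The distribution of subjects over the up to 9 sites is not stated.

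**Conclusion.** The point holds as a defect in the stated scoring rule. Sections 5.1 and 5.3.5 agree with each other, so it is not a slip of wording, and an imaged subject with a positive reading but no AE is scored event-free.

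The size is unknown. The loss is zero if every finding is filed. Under the assumed inputs above, half filing halves the reported rate, from 28.6% to 14.3%. Those figures show how the rule behaves and do not predict this trial's results. A reader might infer that the reported rates will be biased, but that would need evidence that sites leave findings unfiled, and the documents give none.

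The change should be made, but the consequence is limited to secondary, descriptive endpoints; 30-day mortality is unaffected. Confidence is medium, because the endpoint definitions, the imaging section and the imaging form cannot be read.

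**What to change.** In Sections 5.1 and 5.3.5:

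1. Define an endpoint event as a finding on the follow-up imaging assessment **or** a Site-reported AE, with the endpoint definition applied to both sources, so that not every recorded movement counts as migration.
2. Count each event as incident in the window where it is first detected, using the earlier of imaging date and AE onset date. A persistent endoleak is then not counted again as new at later visits.
3. List and query every subject in whom the imaging form and the AE form disagree.
4. Report how many events came from imaging alone.

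If a rule elsewhere already requires an AE for every such finding, cite it in Section 5.3.5 and keep the reconciliation.

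The cost is SAP wording, some programming and some site queries. No new scan or reader is needed, provided the imaging form already captures both findings. Reported endoleak and migration rates may rise.
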